## STRESS AND INFLAMMATION IN THE PATHOPHYSIOLOGY MDD

*A Phase IV, randomized, double-blind, placebo-controlled, one-phase study of the effects of escitalopram and celecoxib on depression.*

## Study Summary

Title	Stress and Inflammation in the Pathophysiology of Depression
Short Title	Stress and Inflammation
IRB Number	819654
Phase	Phase 4
Methodology	Double-blinded study or open-label; Randomized, placebo-controlled, one-phase study
Study Duration	This study will last 6-12 weeks, dependent on whether the participant enters the open-label phase of the study.
Study Center(s)	Single-center.
Objectives	1: Characterize neuroanatomical and neuropsychological correlates of abnormal cytokines in MDD. 2: Characterize the reversibility of brain dysfunction, including cognitive impairment, with treatment of depression and its association with inflammation.
Number of Subjects	100 depressed subjects, 50 control subjects
Main Inclusion and Exclusion Criteria	18-80, depressed, males and females, without psychosis or other concomitant psychiatric illnesses, or significant cardiac, liver, or GI disease.
Drugs	Escitalopram 10 mg/day for 3 days and then 20 mg/day for 39 day (taper down of 10 mg for 3 days) with placebo or Escitalopram 10 mg/day for 3 days and then 20 mg/day for 39 day (taper down of 10 mg for 3 days) with celecoxib (400 mg/day)

CONFIDENTIAL

Duration of administration	6-12 weeks
Statistical Methodology	The design of this trial is simple repeated measures design.
Safety Evaluations	This is a low-risk study. Subject safety will be closely monitored. Subjects reporting of side effects will be used to evaluate individual safety of high doses of escitalopram and celecoxib. Additionally, heart rate monitoring will allow us to assess the safety of celecoxib for blood pressure risks.
Data and Safety Monitoring Plan	The sponsor is responsible for monitoring the data quality and the ongoing safety of subjects. The PI will be monitoring the data quality and the ongoing safety of subjects.

CONFIDENTIAL

This material is the property of the University of Pennsylvania.

## 1 BACKGROUND AND STUDY RATIONALE

This study will be conducted in full accordance with all applicable University of Pennsylvania Research Policies and Procedures and all applicable Federal and state laws and regulations including [as applicable include the following regulations as they apply 45 CFR 46, 21 CFR Parts 50, 54, 56, and 312, and Good Clinical Practice: Consolidated Guidelines approved by the International Conference on Harmonisation (ICH).] All episodes of noncompliance will be documented.

### **1.1 *Introduction***

Major depression (MDD) is a cause of disability worldwide, but the etiology of MDD remains unclear. An emerging concept is that inflammation may have relevance, especially in MDD. We have data supporting increased inflammatory cytokines in MDD compared with controls that are associated with decreased hippocampus and amygdala volumes. MDD also had impairment in neuropsychological function in episodic memory, executive function, decreased hippocampus and amygdala resting state functional connectivity. Antidepressant treatment improved IL-6 levels, neuropsychological testing and resting state connectivity.

We will recruit patients with MDD (n = 100) and controls (n = 50) to characterize immune function, brain structure and connectivity and neuropsychological function. Using the Hospital of University of Pennsylvania's Pepper Lab we will measure participants' c-reactive protein (CRP) levels, and stratify participants according to CRP level (i.e. high (CRP  $\geq$ 3) and low (CRP  $<$ 3)). All participants with MDD (n=100), will receive a selective serotonin reuptake inhibitor (SSRI) antidepressant and we will randomize them to SSRI plus placebo (n $\leq$ 50) or SSRI + celecoxib (n $\leq$ 50). We will assess participants pre- and post-treatment with peripheral and central cytokine levels, neuropsychological tests and brain resting state functional connectivity.

Hypothesis 1: a) Compared with matched controls, MDD will have abnormalities in peripheral and inflammatory cytokines, neuropsychological function, hippocampal, amygdala and prefrontal cortex (PFC) structure and functional connectivity; b) Peripheral/central inflammatory cytokine levels will be associated with volume loss in hippocampus and amygdala; and c) Cumulative duration of depression will correlate with volume loss in hippocampus, amygdala, and PFC. d) Across the lifespan there will be an age effect interaction with depression.

Hypothesis 2: a) Once subjects have completed the antidepressant treatment, they will have greater normalization of IL-6 and IL-10, greater improvements in memory, executive function, and in resting state functional connectivity compared to their baseline measures; b) Improvement in clinical depressive scores will correlate with normalization of inflammatory cytokines; c) Those randomized to the addition of celecoxib (vs placebo) will have additive improvements in cytokines, resting state functional connectivity and depression scores.

## **1.2 Background and Relevant Literature**

Depression is a common cause of morbidity, disability and mortality with an increasing worldwide prevalence. A key distinguishing feature of MDD versus younger MDD is its association with comorbid medical illness, such as vascular diseases often resulting in decreased cognitive function. The etiological factors contributing to MDD are not entirely understood, but the vascular depression hypothesis posits that cerebrovascular disease contributes to the development and severity of depression in older adults by causing ischemic white matter lesions of subcortical limbic structure projections to the frontal cortex or in frontal cortical white matter tracts; these interruptions cause alterations in mood regulation and cognition. In addition, there is mounting evidence that patients with major depression (MDD), particularly those with MDD, have increased oxidative stress, resulting in part from increased peripheral blood inflammatory biomarkers. Compared with nondepressed individuals, those with MDD have elevations of inflammatory cytokines and their soluble receptors in peripheral blood and CSF. Further, they have elevations in blood concentrations of acute phase reactants, including acute phase proteins, adhesion molecules, chemokines, and mediators of inflammation such as nitric oxide synthase (NOS) and prostaglandins. Increased cytokines include interleukin (IL)-1, tumor necrosis factor (TNF) alpha, and IL-6, one of the most commonly and reliably elevated peripheral biomarkers in MDD. In addition to an overall correlation with the depressed state, there are correlations between specific depressive symptoms and inflammatory markers. These include associations of sleep impairment, fatigue and cognitive dysfunction with IL-6. Evidence for an association with depression also includes the ability of proinflammatory factors to induce depressive symptoms, which were correlated with blood cytokine concentrations. In the case of prolonged exposure to cytokines, there is a marked risk of becoming depressed, with approximately 25% of patients exposed to interferon (IFN)- experiencing symptoms of MDD. IL-6 has been shown to interfere with the production of serotonin from tryptophan by increasing breakdown of tryptophan, thus reducing serotonin levels (and increasing depression risk) and preferentially increasing the synthesis of kynurene and its neurotoxic metabolites, 3-hydroxykynurene and quinolinic acid. IL-6 drives this metabolic shunt and IL-10 partially counters it.

Further, the inflammation hypothesis of aging proposes an age-related increase in cytokine production, resulting in a chronic proinflammatory state, which has a detrimental effect on cellular function. Elevated plasma IL-6 is a common finding in older adults who are at greater risk of disease and disability. Given the strong correlation between proinflammatory markers and illness, inflammation is particularly important in MDD. Increased plasma IL-6 is a risk factor for many diseases of aging, including hypertension, atherosclerosis, cardiovascular ischemia and type 2 diabetes, all of which are more common in MDD. IL-6 was called the gerontologists cytokine by William Ershler, who proposed that this cytokine regulates a key human aging pathway, given the consistent association between elevated plasma IL-6 and poor health outcomes. In healthy older adults elevated plasma IL-6 has a linear inverse correlation with cognitive performance. A sizeable and growing number of older people are at risk for IL-6 mediated cognitive effects. Chronically elevated IL-6 is associated with mild cognitive deficits,

CONFIDENTIAL

even in apparently healthy community dwelling elders. Elevated IL-6 augments the risk of stroke and dementia and predicts future cognitive decline. Despite this evidence of a link between plasma IL-6 and CNS impairment the specific mechanisms remain largely unknown. We believe it is likely that with each repeated episode of depression and resultant exposure to elevated inflammatory cytokines in brain, there is progressive regional loss of inhibitory neurons in brain regions that are particularly sensitive to inflammatory damage, such as the hippocampal CA2-3 region. We hypothesize that this volumetric loss is critically associated with development of brain dysfunction and risk of repeated depressive episodes.

A meta-analysis (1) that included 14 trials and 6262 participants was recently conducted to examine the use of non-steroidal anti-inflammatory drugs (NSAIDs) and cytokine inhibitors. The pooled effect estimate suggested that anti-inflammatory treatment reduced depressive symptoms compared with placebo. Subanalyses emphasized the antidepressant properties of celecoxib on remission and response, particularly in combination with antidepressant. Among the 6 studies that reported adverse events there was no evidence of an increased number of GI or cardiovascular events after 6 weeks or infections after 12 weeks.

A meta-analysis of five (2) post-approval clinical trials associated lower depression scores with celecoxib treatment, 200 mg qd over 6 weeks, in patients with active osteoarthritis, n=607, compared to patients exposed to placebo (2). These clinical trials were highly protected against bias by following a multicenter, randomized, double-blinded, placebo-controlled, active-comparator, parallel-group design (2). The authors write that a significant increase in systolic or diastolic blood pressure and heart rate was not evident after 6 weeks of celecoxib treatment (2). This supports a good safety profile for this celecoxib dosing regimen, in particular, when considering that 48% of patients (291/607) had hypertension at baseline, 20% (121/607) hyperlipidemia, and 17% (103/607) diabetes mellitus as baseline conditions. The high morbidity is also reflected in that 51% (310/607) of patients report at baseline to receive pharmacotherapy to treat cardiovascular disease (2). CRP levels have been shown to highly correlate with cytokine levels. Validation of commercially available methods of CRP has been conducted and shown that semi-quantitative CRP strips can distinguish between normal and high levels of CRP within individuals very simply (3).

### **1.3 Name and Description of the Study Drugs**

Study drug intervention consists of escitalopram and celecoxib in doses approved for clinical use. Dose ranges for escitalopram are 10-20 mg/day. The dose of celecoxib is 400 mg/day.

## **2 Study Objectives and Investigational Plan**

Aim 1: Characterize neuroanatomical and neuropsychological correlates of abnormal cytokines in MDD.

CONFIDENTIAL

Aim 2: Characterize the reversibility of brain dysfunction, including cognitive impairment, with treatment of depression and its association with inflammation.

**2.1 Primary outcome variable(s)\***

- 1) Cytokine levels will be measured in blood: Primary measure will be IL-6 pre- and post-treatment.
- 2) Hippocampus, including subvolume analyses and Amygdala volumes: Left and right volumes will be separately measured and standardized by brain volumes before being entered in analyses. Prefrontal cortical thickness: L & R orbitofrontal, superior frontal and frontal pole.
- 3) Antidepressant treatment response determined using the MADRS score following antidepressant treatment covaried on baseline MADRS score.
- 4) Neuropsychological function as determined by factor scores from episodic memory and executive function.
- 5) Resting state functional connectivity of the hippocampus and amygdala to anterior cingulate (AC) and dorsolateral prefrontal cortex (DLPFC).

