Hypothesis 1b: Cytokine levels will be correlated with hippocampal and amygdala volumes and PFC thickness; To examine correlational hypothesis 1b, we used a Fisher's r-to-Z transformation test for a correlation between IL-6 and volumetric measures. To achieve 80% power with a two-tailed Z test and 5% significance level, a correlation of |.23| can be detected for a sample of 150 subjects. Based on our preliminary data for IL-6 and for left CA2-3 we have a correlation of .33.

Aim 2: Characterize the effects of treatment on depression and the association with inflammation. Hypothesis 2a: Subjects randomized to treatment will have greater normalization of IL-6 and functional connectivity compared to those randomized initially to placebo. To achieve 80% power with a two-tailed t-test and 5% significance level, a mean difference of 2.1 can be detected with a standard deviation of 3.6 for a sample of 50 medicated and 50 nonmedicated subjects. Based on our preliminary data for IL-6, the mean (SD) difference, between the nonmedicated and medicated group for IL-6 is 2.7 (3.6). We will test Hypothesis 2a for improvement in functional connectivity with repeated measures ANOVA with the treatment group x time interaction result testing whether improvement in the outcome variables (increase in hippocampus and amygdala connectivity to DLPFC and AC) is greater in the treatment group than the placebo group, over and above non-specific changes over time (e.g., practice effects, naturalistic changes) that would be seen also in the control group. Our sample size of 100 with 50 in each group provides 80% power to detect a moderate effect size of .38 with .7 intraclass correlation on the group x time interaction, based on a two-tailed F-test with 5% significance level and assuming 10% attrition.

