## 5.2 Recruitment, screening and baseline assessments

Brief Summary of Procedures (also see attached schedule of procedures and assessments):

Potential participants will be recruited from the community or they may be approached by collaborating clinicians or research team members (see recruitment plans) to explore potential participant's interest in taking part in a research study. Those who are interested will receive a telephone call from research staff to conduct a telephone screen. Those who pass the phone screen will receive an appointment to come to the research location to review and sign the informed consent form for screening purposes and to complete baseline diagnostic assessment screen, blood draw to test for CRP level, Hepatitis B and C, HIV, and rheumatoid arthritis, and will also complete an EKG to determine eligibility. Those who are eligible will return for a baseline visit and will review and sign another informed consent form for participation in the full protocol. Once fully consented, participants will undergo a series of visits to conduct multiple assessments which will include:

- (1) Psychological and Neuropsychological Tests at baseline and week 6; Open Label at week 6;
- (2) Medical Examination;
- (4) 3-4 Blood Collections (blood draw at screening, blood draw at baseline, blood draw at week 2 for liver function and hematocrit assessment, and one at Week 6) for those who enter the open-label phase they will receive an additional 2 blood draws (one at Open Label Week 2 to assess for liver function and hematocrit levels, and one at Open Label Week 6). All participants will be asked if willing to participate in additional blood collection for immune profiling.
- (5) 2-3 MRIs, one at baseline, one at week 6, and one at open-label week 6; the baseline scan will occur before treatment begins;
- (6) 2-3 fMRI (one at baseline which will occur during the same baseline MRI session, one at Week 6, and one at open-label week 6);
- (7) Optional Nutrition Assessment. Participants will be asked to do a 24-hour dietary recall. The food recall will also be collected using the Nutrition Data System for Research (NDSR). Participants are guided through a multiphase interview where they are guided to recall all the food they ate in the preceding 24 hours.

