#### **5.4 Blood draws**

During the screening visit, all participants will have a blood draw to test for CRP levels to stratify the participants accordingly in High CRP and Low CRP groups. Participants will also have a blood sample drawn at the end of the screening visit to test immediately for Hepatitis B and C, HIV, autoimmune diseases (double-stranded DNA test), and rheumatoid factor; as well as to use in later analyses of inflammatory markers. Participants will have a blood sample drawn (approximately 16.5mL) at the screening visit, approximately 40 mL at the baseline visit, approximately 40 mL at the end of the study, 40 mL at the end of the open label phase. Blood samples will be used for doing tests for inflammatory markers and for measuring levels of Interleukin-6, Interleukin-10, TNF-alpha, and C-reactive protein. We will look at immunological markers by two methods; luminex and flow cytometry. The Luminex assay measures soluble proteins in the sera. Molecules such as IL-6 and TNF-alpha, MIP1-alpha, IFN-alpha, CRP will be assessed. We will include or alter molecules in the luminex assay based on the most recent literature as we near the end of sample collection. Flow cytometry will also be utilized. Flow cytometry will be used to measure the status of T cells which are important in suppressing such conditions as infectious disease and cancer. We will develop a series of markers that define the memory and naive phenotype of T cells along with their activation status and functionality. We will also assess additional cell subsets such as NK and macrophages. Molecules that will be assessed include but are not limited to; CD3, CD4, CD8, CD45RO, CD27, CCR7, CD69, CD33, CD68, CD56, CD16, CD38 and HLADR and CD11c -monocytes. Some blood will be retained and banked for future research. Additional blood is being collected for ex vivo isolation of human peripheral blood mononuclear cells (PMBC), which is another assessment of inflammation levels. This additional blood draw will be optional and offered to all depressed participants.

Participants will give blood for a liver-function test and for hematocrit levels to test for GI bleeding. Participants may also have 24-hour ambulatory blood-pressure monitoring. Participants may wear a cuff for 24 hours that is set to automatically take blood pressure every 15 minutes during the day and every 30 minutes during the night.

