## **6 Analysis Plan**

### **6.1 Data Analysis and Predictions**

At a basic level, the design of this trial is simple repeated measures design with a) two replicates (time points) b) baseline covariates and outcomes, and c) a single between-person factor (initial case-control depression status). The data collected at two time points to be included in analysis (pre- and post-treatment) will be the depression severity, inflammatory markers, resting state functional connectivity and neuropsychometric data. There have been no published studies to date examining adjuvant celecoxib and SSRI treatment in patients who simultaneously received assessment of inflammatory biomarkers. However, based on our own small pilot sample we will have greater than 85% power to detect differences in changes in IL-6 between SSRI responders and SSRI + celecoxib responders. Volumetric data and confounders to be included in the analysis will be collected at baseline. Classic models of change scores can be used where the baseline level can be controlled giving the so-called residual change score. Use of residualized change scores has several analytic advantages: (1) control for variance (the best predictor of today's value is yesterday's value), (2) statistically each subject is started at the same point. Thus, our estimation model will be extended from the classic model of change scores to a repeated measures ANOVA (analysis of variance) or mixed model repeated measures design. A joint modeling approach with mixed models for repeated measures data can be used to address within-subject variation and between-subject variation of the repeated measurements of multiple

CONFIDENTIAL

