## 12 Appendix

### 12.1 Study Flow-Chart

Procedures conducted with all participants				
Procedure	Phone Screen	In-person Screen	Baseline	Week 6
Informed Consent		X (Initial screening consent)	X (Full study consent)	X
Verbal Consent	X			
Screen, History (include GI/bleeding risks)	X			X
Screen, History, SCID, MADRS, HAMD, CGI, MOCA		X		
EKG		X		X
PE , Laboratory tests, including IL-6, IL-10, CBC with diff;		X	X	X
MRI; structural and functional			X	X
Lifetime depression, PSS, LES score			X	
Framingham VRF, CIRS-G, QOL		X		X
Neuropsychological tests (COWA, Trails A & B, WLMT, Digits Forward, Digits Backward, Digits Ascending, MMSE, Logical Memory, Digit Symbol, Benton Visual Retention, Shipley Vocabulary, Boston Naming, CogState)			X	X

\*.

CONFIDENTIAL

This material is the property of the University of Pennsylvania.

Additional procedures conducted with depressed participants initially randomized to celecoxib:					
Procedure	Study Visits				
	Baseline	Wk 1	Wk 2	Wk 4	Wk 6
Concomitant Medications	X	X	X	X	X
Drug Dispensed Escitalopram + celecoxib or escitalopram + placebo (weeks 0-6)	X	X	X	X	X
Psychiatrist evaluation, depression scales, Vital Signs (including optional urine samples at baseline, week 1 or 2, and 6; triplicate in-office BP weekly and monitor GI-pain/bleeding for safety ),AEs, SAEs	X	X	X	X	X
PE (Lab tests including IL-6, IL-10, CBC with diff)	X	X	X	X	X
Liver function test & GI/bleeding risks	X		X		
Actigraphy (1 consecutive day minimum, optional longer),		X	X	X	
Optional Stool Sample	X		X		X
Optional Saliva samples	X	X	X	X	X
Safety (ABPM, FOBT and/or hematocrit levels)	X		X		
Safety (24-hour dietary recall, optional counseling on sodium-deplete diet)	X	X			

CONFIDENTIAL

This material is the property of the University of Pennsylvania.

	Additional procedures conducted with depressed participants initially randomized to placebo:									
	Procedure			Phase 1			Open Label Phase			
	Baseline	Wk 1	Wk 2	Wk 4	Wk 6	Wk 1	Wk 2	Wk 4	Wk 6	
Concomitant Medications	X									
Drug Dispensed Escitalopram + celecoxib or escitalopram + placebo (weeks 0-6) (Open label- Escitalopram + celecoxib)	X	X	X	X	X	X	X	X	X	
Psychiatric evaluation, depression scales, Vital Signs (including optional urine samples at baseline, week 1 or 2, and 6; triplicate in-office BP weekly and monitor GI-pain/bleeding for safety ),AEs, SAEs	X	X	X	X	X	X	X	X	X	
Liver function test & GI/bleeding risks	X		X				X			
Actigraphy	X	X	X	X	X	X	X	X	X	
Optional Saliva samples	X	X	X	X	X	X	X	X	X	

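### IL-6 is scheduled twice before treatment but the plan uses one pre-treatment value; adjusting the randomised contrast for both draws is a cheap precision gain of uncertain size

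*Combined protocol and SAP*

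**What the plan says.** Section 2.1 lists blood cytokines first among the primary outcomes: "Primary measure will be IL-6 pre- and post-treatment". Section 6.2 item 1 repeats this, and 6.1 describes a repeated measures design with two time points, before and after treatment. None of the three names the draw that supplies the earlier value. Section 1.1 (Hypothesis 2a) and section 6.3 (Hypothesis 1a) speak of baseline measures, again without naming a draw.

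The schedule has two candidates. In the flow chart for all participants (12.1), the row with "Laboratory tests, including IL-6, IL-10, CBC with diff" is marked at the in-person screen, at baseline and at week 6. Section 5.2 lists "blood draw at screening, blood draw at baseline" as separate collections. Section 5.4 says the screening sample is for infection and autoimmune testing "as well as to use in later analyses of inflammatory markers", and that the CRP stratum is assigned from the screening draw.

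The model is left open. Section 6.1 says "Classic models of change scores can be used where the baseline level can be controlled giving the so-called residual change score", then extends this to a "repeated measures ANOVA (analysis of variance) or mixed model repeated measures design". The only within-person correlation in the documents is in 2.7, where the connectivity calculation assumes a "moderate effect size of .38 with .7 intraclass correlation on the group x time interaction".

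**The concern.** A single IL-6 value carries within-person noise. Where two untreated values exist for each randomised participant, adjusting for both usually explains more of the week 6 variance than adjusting for one. Neither value can be affected by treatment, so the gain carries no risk of bias in the arm comparison. Naming the draw also removes any question of which pre-treatment value was meant once assay results are in hand.

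The choice matters differently outside the randomised contrast. Participants are classed as high or low CRP on the screening draw, section 2.5 targets 50 of each, and section 1.2 says CRP correlates highly with cytokine levels. If that target over-represents high CRP, screening IL-6 would be expected to drift back towards the mean before any treatment. In the randomised contrast the drift is shared by both arms. In a paired pre-post test, a change-score model or the depressed-control comparison it would not cancel.

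**Working it through.** **The plan's own figure.** Section 2.7 (Aim 2) gives a detectable IL-6 difference of 2.1 with SD 3.6, 50 v 50, two-sided 5%, 80% power.

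- Normal approximation: (1.960 + 0.842) × 3.6 × √(2/50) = 2.02. Noncentral t: 2.04. Power at 2.1 is 83.1% and 82.3% respectively.
- With the 10% attrition that 2.7 assumes for connectivity (45 per arm): 2.13 and 2.15; power 79.0% and 78.1%.

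So 2.1 is about right. It comes from a plain t-test with no covariate.

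**Set-up.** Assume equal variance (taken as 1) at every draw. Let r be the correlation of each pre-treatment draw with week 6, and q the correlation between screening and baseline.

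| Error variance | One pre value | Mean of both |
|---|---|---|
| Change score, or two-time-point repeated measures ANOVA | 2(1 − r) | 1 + (1 + q)/2 − 2r |
| ANCOVA (residualised change) | 1 − r² | 1 − 2r²/(1 + q) |

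When both draws share the same r, entering them as two covariates gives the same residual variance as their mean.

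**Equal correlations (q = r).** At r = .7, the connectivity value borrowed for illustration:

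- Change score: .60 to .45, a 25% fall. The formula becomes 1.5(1 − r), so the fall is 25% at any r.
- ANCOVA: 1 − .49 = .51 to 1 − .98/1.7 = .424, a 17.0% fall.
- A simulation (4000 trials, 50 per arm) gave falls of 26.5% and 18.1%.

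ANCOVA falls at other values of r: .3, 5.3%; .5, 11.1%; .6, 14.1%; .8, 19.8%.

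**Pre-treatment draws closer to each other than to week 6.**

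| r | q | Change-score fall | ANCOVA fall |
|---|---|---|---|
| .7 | .8 | 16.7% | 10.7% |
| .7 | .9 | 8.3% | 5.1% |
| .5 | .8 | 10.0% | 3.7% |
| .5 | .9 | 5.0% | 1.8% |

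**Screening tracks week 6 less well than baseline does.** Take .6 for screening with week 6, .7 for baseline with week 6, and q = .8.

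- Simple mean, change score: 1 + .9 − 1.3 = .60, against .60 for baseline alone. No gain.
- Simple mean, ANCOVA: 1 − .65²/.9 = .531, against .51. A 4% loss.
- Both draws as separate covariates: R² = (.49 + .36 − 2 × .7 × .6 × .8)/(1 − .64) = .178/.36 = .494, so the residual is .506 against .51. A gain of just under 1%.

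Separate covariates let the data weight the draws. A forced mean does not.

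**What this means for the detectable difference.** If 3.6 is the SD of the quantity analysed with one pre value, then at 50 per arm a 17% cut takes 2.04 to 2.04 × √.83 = 1.86 and power at 2.1 from 82% to 89%. A 5% cut gives 2.04 × √.95 = 1.99. If 3.6 is instead the raw outcome SD, then at 45 per arm and r = .7 the ANCOVA figure moves from 2.15 × √.51 = 1.54 to 2.15 × √.424 = 1.40. Either way, a 17% variance cut lowers the detectable difference by 1 − √.83 = 9%.

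**Cost.** With 100 participants, the residual degrees of freedom go from 97 (intercept, arm, one covariate) to 96.

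**The case against.** A reader might infer that the plan leaves its primary baseline wholly open, that it throws the screening value away, and that averaging would save 17 to 25% of the variance for nothing. The documents do not support any of these as stated.

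- **Open baseline.** There is a named baseline visit with its own draw, and 1.1 and 6.3 use the word baseline. The natural reading is that draw, and using it alone is standard and unbiased.
- **Discarding.** No section says so. Section 5.4 keeps screening blood for marker analyses; the analysis text is simply silent on its role.
- **17 to 25%.** The .7 is stated for connectivity, and the figure also needs the screening-baseline correlation to equal the correlation with week 6. Two untreated draws could well be closer to each other than to a value after six weeks of treatment. The screening-to-baseline interval is not fixed, and the documents do not say whether the psychotropic washout is complete at the screening draw, so the two values may not be exchangeable.
- **Whether both assays exist.** The flow-chart row bundles examination and laboratory tests. A similar row is marked at weeks 1, 2 and 4 for the celecoxib arm, although 5.2 lists no week 1 or 4 draw and limits week 2 to liver function and hematocrit. The screening sample is also smaller (about 16.5 mL against about 40 mL) and shared with other tests.

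All four stand as limits on size and certainty. They do not remove the point: the schedule and 5.4 together support a second pre-treatment IL-6 value, and doubts about spacing or washout affect how much precision is gained, not the validity of the arm contrast.

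**Conclusion.** The point holds as a conditional efficiency gain together with a clarification. Using both pre-treatment values in the randomised celecoxib-placebo contrast cannot bias it. The ANCOVA variance falls by about 5 to 20% for equal correlations of .3 to .8, by about 4 to 11% in the main cases where the untreated draws are closer to each other than to week 6, and by close to nothing in the least favourable cases. The 25% applies only to a change-score analysis with equal correlations, and 6.1 does not commit to that model. At r = .7, ANCOVA with one value (.51) already beats the change score with one value (.60).

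These figures rest on equal variances at the three draws and on assumed correlations, since none is given for IL-6. Because a simple mean can lose precision, separate covariates are the safer form. Outside the randomised contrast the screening value should stay out, because the CRP stratum is assigned on that draw.

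**What to change.** In 6.2 item 1, with a cross-reference from 2.1, state before unblinding:

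- For the randomised celecoxib-placebo contrasts in IL-6 and IL-10, the model adjusts for the screening and baseline-visit values as two separate covariates, on the scale used for analysis (transformed, if 6.1 leads to a transformation). If one value is missing, the available one is used. The mean of the two is an acceptable alternative if both draws are about equally correlated with week 6.
- For the Hypothesis 1a depressed-control contrast, the paired pre-post test and the Hypothesis 2b change models, the pre-treatment value is the baseline-visit draw only.

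Confirm at the same time that IL-6 and IL-10 are assayed on the screening sample, as the flow chart indicates. The cost is a few sentences and one covariate degree of freedom. No draw or visit is added.
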